that morning. After collecting vitals and testing a urine sample for pregnancy and to confirm abstinence from illicit drugs, participants will receive 50% of their prescribed methadone dose, which will be prepared by the BPRU pharmacy, to consume under staff observation at BPRU. This dose will produce modest suppression of participant opioid withdrawal for an acute period of time, which will provide an opportunity for them to become acquainted with the session procedures while still ensuring they will show prominent signs of withdrawal during the study period. Initial vitals and urine testing will take place at the BPRU. The participant then will be transferred to the CRU where they will remain until the end of the 3rd day. Participants will be assessed for symptoms of opioid withdrawal and complete measures of drug craving and anxiety periodically throughout Day 1. The first dose of study drug (placebo or Epidiolex) will be administered in the afternoon (e.g., 18:00 +/- 1:00 hour) on Day 1 at the CRU.

Participants will complete withdrawal ratings on a regular basis (e.g., every 4 hours) before and after study drug administration, except for when the participant is sleeping. This schedule will be based on the pharmacokinetic profile of CBD (21). Vital signs will also be measured every time withdrawal assessments occur (Figure 1).

[figure not shown]

Figure 1. Timeline of inpatient session with approximate timing for study procedures. Gray circles indicate when measures of opioid withdrawal. craving. and anxietv are assessed.

On Day 3, participants will complete a cue-induced craving task and a Cue-concurrent Choice Task, and a Methadone Valuation Task described below. Withdrawal ratings will continue up to study discharge on Day 3 and acceptability ratings of the study drug will be collected prior to discharge. Participants will be discharged in the afternoon on Day 3, one hour after finishing the Methadone Valuation Task. At any point a participant can elect to resume regular methadone dosing and remain at the unit to complete study participation. However, participants who take their dose before beginning the Methadone Valuation Task he or she will not be able to participate in the Methadone Valuation Task. Finally, before participants leave, medical staff will collect a blood sample to be tested for liver enzyme levels. For an overview of study procedures, please reference Figure 1.

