#### Exclusion Criteria:

- Meet DSM-5 criteria for past year alcohol/substance use disorder other than opioid use disorder
- Previous adverse reaction to a cannabinoid product
- Urine sample that tests positive for drug other than methadone
- Self-report any illicit drug use or cannabinoid use in the past 7 days
- Presence of any clinically significant medical/psychiatric illness judged by the investigators to put subject at elevated risk for experiencing an adverse events
- Past year suicidal behavior as assessed via the Columbia Suicide Severity Rating Scale
- History of seizure disorder
- Past 14 day use of any of the following contraindicated medications:
  - o Clobazam, Valporate
  - Moderate or strong inhibitors of CY3A4 or CYPC19 (with the exception of methadone)
  - Strong CYP3A4 or CYP2C19 inducers
  - UGT1A9, UGT2B7, CYP1A2, CYP2C8, CYP2C9, CYP2C19 substrates (with the exception of caffeine).
  - CNS depressants that are contraindicated with Epidiolex
- Breathalyzer that tests positive for alcohol prior to session admission
- Self-reported consumption of grapefruit juice within 24 hours of session admission
- Have a history of clinically significant cardiac arrhythmias or vasospastic disease
- Have circumstances that the study investigators believe are contraindicated with study participation and/or would interfere with study participation (e.g., impending jail).
- Moderate-severe hepatic impairment as indicated by ALT or AST levels > 3x ULN and/or Bilirubin levels >2x ULND as evidenced by a blood test.

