#### N/A

#### 7. Study Statistics

a. Primary outcome variable.

Feasibility:

- Number of participants who complete the study as intended
- Peak change in withdrawal scores (Subjective Opiate Withdrawal Scale; SOWS) during abstinence-induced withdrawal- this will provides evidence that withdrawal will be sufficiently quantifiable to use this model to examine Epidiolex suppression of withdrawal in a large-scale R01-type trial.

Safety:

- Frequency of Adverse Events (excluding symptoms of opioid withdrawal) reported under each condition (0, 800mg CBD)
- Number of participants whose AST/ALT levels >3xULN at the end of the session according to a blood test at the end of the active drug condition

Initial Efficacy:

- Efficacy will be assessed by comparing the following outcomes between the active (CBD) and placebo-dosing sessions:
  - Withdrawal symptom suppression, measured through daily self-report ratings of withdrawal on the SOWS, evaluated as Total score and individual scores. Scores will be evaluated using area-under-the-curve for each day as well as peak daily rating.
  - Number of 30-minute intervals for which the participant selected money over methadone during the methadone evaluation task

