# b. Secondary outcome variables.

Acceptability:

- Percent of participants who would recommend their medication to a family member or friend trying to taper down from opioid medications
- Visual analog ratings of the degree to which the medication suppressed opioid withdrawal symptoms
- Participant rating of medication acceptance on a 5-point acceptance rating scale
- Attentional bias measured by the visual probe task and the cue-concurrent choice task
- c. Statistical plan including sample size justification and interim data analysis.

This is a within-subject pilot study to support an R01 trial. Results will be primarily evaluated descriptively because the study will not be sufficiently powered or designed for formal betweengroup testing. Outcomes described above will be used as preliminary data within an R01 application.

d. Early stopping rules.

Participants will be discharged from the study if they leave the residential unit against medical advice, request to be removed from the study, express suicidal thoughts, are noncompliant with study tasks, or if new information becomes available to suggest this study may cause them more than minor harm.

The study will be stopped if any of the following criteria are met: 1) participant death during participant or 2) five participants have AST/ALT values 3X ULN at the end of the study relative to baseline (collected at screening) levels.

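### The only liver outcome is a count of AST/ALT above 3xULN on CBD, so a consistent rise within participants can be reported as few or no events

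*Combined protocol and SAP*

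**What the plan says.** Section 2 makes the safety of the drug within the withdrawal paradigm the first objective. Section 7a gives two safety outcomes: adverse event frequency in each condition, and "Number of participants whose AST/ALT levels >3xULN at the end of the session according to a blood test" taken "at the end of the active drug condition". The second is the only liver outcome; section 7b has none.

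The measurements carry more information than that. Section 4a (Session Procedures) says that "before participants leave, medical staff will collect a blood sample to be tested for liver enzyme levels". Section 7d shows that baseline enzyme levels come from screening, but uses them only in a stopping criterion, itself a threshold count: "five participants have AST/ALT values 3X ULN at the end of the study relative to baseline (collected at screening) levels".

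Section 5 excludes "Moderate-severe hepatic impairment as indicated by ALT or AST levels > 3x ULN", so the laboratory criterion admits values up to the same figure that defines the outcome. Section 8a ties that figure to the product label as a definition of hepatic impairment for exclusion. No reason is given for making it the sole liver outcome. Section 7c says that results will be evaluated mainly descriptively, and gives no sample size, alpha or test.

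**The concern.** AST and ALT are continuous, and each participant serves as their own control. The outcome keeps one yes/no fact per person and discards the size of the change. A participant going from 2.8 to 3.1xULN, a rise of 11% (3.1/2.8 = 1.11), is an event. A participant going from 0.5 to 2.9xULN, a 5.8-fold rise (2.9/0.5), is not. The count can mislead in both directions.

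Section 7a treats its other measured scale differently: SOWS scores are kept as area under the curve and daily peak, and compared between sessions. The liver values get neither treatment.

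At stake is what the pilot can say about liver safety. Section 7c makes the listed outcomes the preliminary data for the grant application. A zero or near-zero count could be read there as no effect on the liver when the paired values show a consistent rise.

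**Working it through.** The documents state no figure to reproduce, so there are three checks.

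**1. Rise needed to count as an event.** Fold rise needed = 3 / (starting level in xULN).

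| Start (xULN) | Fold rise needed |
|---|---|
| 0.5 | 6.0 |
| 1.0 | 3.0 |
| 1.5 | 2.0 |
| 2.0 | 1.5 |
| 2.9 | 1.03 |

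If everyone starts at or below 1.0xULN and doubles, nobody exceeds 2.0xULN and the count is zero. This needs no assumption beyond the starting level.

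**2. Chance of a zero count under a true rise.** Every input here is an assumption: 10 to 20 participants; log-normal enzyme values with median 0.6 or 1.0xULN; between-person SD of the log 0.5; SD of the CBD-minus-placebo log difference 0.3 to 0.5; screening values above 3xULN excluded; the same fold rise for everyone on CBD. One enzyme is modelled. If a rise in either enzyme counts, zero is somewhat less likely than shown. Simulated results:

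| True rise | Median 0.6xULN | Median 1.0xULN |
|---|---|---|
| 1.5-fold | 63-89% | 10-42% |
| 2-fold | 26-64% | at most about 10% |

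High ends are 10 participants with the smaller SD; low ends are 20 with the larger.

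Hand check of one cell, ignoring the entry limit (1.5-fold, median 0.6, difference SD 0.3, 10 participants):
- Per-session SD = 0.3/√2 = 0.212; total SD = √(0.5² + 0.212²) = 0.543.
- z = ln(3/(0.6 × 1.5))/0.543 = 1.204/0.543 = 2.22, so the chance of an event per person is about 0.013.
- Chance of none in 10 = (1 − 0.0133)^10 = 0.87. The entry limit raises this slightly, to the 89% in the table.

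A further run used per-session SDs of 0.2 to 0.3 (difference SD 0.28 to 0.42), with 10 or 20 participants and a median of 0.6xULN. Zero events then occur in about 94-99% of trials with no drug effect and 67-88% with a 1.5-fold rise. At that baseline a zero count barely separates the two.

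Zero is also weak reassurance about the event rate itself. The one-sided 95% upper limit is 1 − 0.05^(1/N): 26% for 0/10 and 14% for 0/20.

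**3. What the same samples give on the full scale.** With d = ln(CBD value / placebo value) per participant, the geometric mean ratio is exp(mean d). Its 95% CI multiplies and divides that ratio by exp(t × s/√N).
- N = 10, s = 0.5: exp(2.262 × 0.5/√10) = 1.43. An observed ratio of 1.5 has CI 1.05 to 2.14.
- N = 20, s = 0.3: exp(2.093 × 0.3/√20) = 1.15. An observed ratio of 1.5 has CI 1.30 to 1.73.

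A ratio of 1.3 in the less favourable case has a lower limit of 1.3/1.43 = 0.91, so small rises can stay uncertain on this scale too.

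**The case against.** The strongest reply is that this is a descriptive pilot with a clinical safety aim. It is not a study to estimate a mean enzyme effect. The 3xULN figure recurs in the entry criterion, the stopping rule and the label definition, and one clinical flag used throughout is defensible. Nothing in section 7a forbids tabulating the values. Medical clearance and investigator judgement in section 5 may keep people near the limit out. An enzyme rise judged to be an adverse event would be compared with placebo.

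Much of this stands. The flag is sensible and should stay, the values are not lost, and the starting levels of 2.8 and 2.9xULN are extremes. It does not remove the point. The named descriptive quantity is still the count, no rule makes an enzyme rise an adverse event, and no listed outcome shows the change.

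Three stronger readings are tempting and are not supported:
- A reader might infer that the count will probably be zero whatever happens. At a median of 1.0xULN zero is the less likely result, and after a doubling about 2 to 5 events would be expected.
- A reader might set the power of a paired analysis against a McNemar test of the flags. The plan specifies no test and counts only the active condition, so such a contrast would illustrate lost information and nothing more.
- A reader might conclude that the grant application will report no liver signal. The documents leave the investigators free to show the values.

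**Conclusion.** The point holds as a weakness in how the outcome is defined. Followed as written, section 7a can report few or no liver events despite a consistent rise within participants, and can count a trivial rise in someone admitted just under the limit. That follows from the text and simple arithmetic.

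How often it would happen cannot be settled from the documents, which give no sample size, baseline distribution, variability or expected effect. Under the stated assumptions, a zero count is likely at low baselines with a 1.5-fold rise. It is uncertain at low baselines with a doubling, and unlikely when the median is near 1.0xULN and values double. Nothing in the documents says that CBD raises enzymes by these amounts after four doses. The change is worth making because liver safety falls under the first objective and the remedy is cheap.

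**What to change.** Keep the >3xULN count and add to section 7a, Safety, wording such as:

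> AST and ALT will also be summarised descriptively in multiples of ULN. Individual values will be shown at screening and at the end of each session, with the fold-change from screening. The within-participant ratio of CBD-session to placebo-session values will be given as a geometric mean ratio with 95% CI.

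Base the liver conclusion on both the count and this summary.

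First confirm that the pre-discharge sample in section 4a is taken in both sessions. The session description reads that way, but section 7a mentions a test only for the active condition. If only the active session is sampled, report individual values and fold-change from screening. These have no placebo comparison, so they cannot separate the drug from other effects of the session.

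Cost: a few lines of text and a small table. No extra draw, visit or participant is needed if both sessions are already sampled; otherwise the ratio would require placebo-session draws. The downside is one more safety summary, and small rises of no clinical importance become visible.

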#### 2. Objectives

The objective of this research study is to collect data to support a NIDA grant application. Data collected for this study will establish: (1) the safety of administering two dosing regimens of Epidiolex within our withdrawal paradigm and (2) the feasibility of our withdrawal paradigm for demonstrating clinically meaningful increases in withdrawal.

**3. Background** (briefly describe pre-clinical and clinical data, current experience with procedures, drug or device, and any other relevant information to justify the research)

The increasing prevalence of opioid use disorder (OUD) is a public health crisis contributing to substantial economic and societal burden. The treatment of OUD, even with the most efficacious interventions, is characterized with high rates of relapse (i.e., > 50% relapsed within 6 months of treatment initiation). Managing withdrawal is critical for ensuring successful treatment retention and outcomes . Adjunctive pharmacotherapy is one way to address persistent opioid withdrawal symptoms and craving. Based on preclinical research and emerging human research, cannabidiol (CBD; a major constituent of the cannabis

plant) is a promising pharmacotherapy for the treatment of OUD. There is preclinical support that the endocannabinoid system is influential in the expression of opioid withdrawal. Cannabinoid type 1 (CB1) receptors are co-localized with mu-opioid receptors and cannabinoid agonists and endocannabinoid catabolic enzyme inhibitors have all shown evidence for opioid withdrawal suppression.

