c. Plan for reporting unanticipated problems or study deviations.

All study events will be monitored during weekly meetings between the study investigators and we will follow all IRB guidance and recommendations regarding the reporting of unanticipated problems of study deviations. All such problems and deviations will be documented and if they do not meet the criteria for immediate reporting, they will be submitted to the IRB as part of the continuing review (or when otherwise requested).

d. Legal risks such as the risks that would be associated with breach of confidentiality.

Participants are all receiving methadone for the purpose of OUD outside of the study activities, and we do not believe this study poses any legal risks associated with breach of confidentiality.

e. Financial risks to the participants.

Participants will not incur any cost for study participation. All study medications will be provided to them at no cost.

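### The primary liver outcome in section 7a is counted after the active session only, so it gives neither an active-placebo comparison nor a size of change

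*Combined protocol and SAP*

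**What the plan says.** Section 7a lists two primary safety outcomes. The first is "Frequency of Adverse Events (excluding symptoms of opioid withdrawal) reported under each condition (0, 800mg CBD"), so adverse events are summarised for placebo and for cannabidiol. The second is the number of participants with "AST/ALT levels >3xULN at the end of the session according to a blood test at the end of the active drug condition", so liver enzymes are summarised for cannabidiol alone, as a threshold count. The initial efficacy outcomes in the same section are compared between the two sessions.

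The relevant surrounding text is as follows.

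- **Section 4a, Session Procedures:** each participant has one active and one placebo session, in randomised and counterbalanced order, and blood for liver enzymes is taken before the participant leaves. The text does not restrict this draw to the active session. Only vital signs and urine tests are described at admission, with no liver draw.
- **Section 4a, Study Design Overview:** the sessions are at least one week apart.
- **Section 5:** ALT or AST above 3x ULN at screening is an exclusion. Section 8a attributes that limit to the product label.
- **Section 7c:** "Results will be primarily evaluated descriptively", and "Outcomes described above will be used as preliminary data within an R01 application".
- **Section 7d:** the study stops if "five participants have AST/ALT values 3X ULN at the end of the study relative to baseline (collected at screening) levels".

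**The concern.** The first aim in section 2 is to establish "the safety of administering two dosing regimens of Epidiolex within our withdrawal paradigm". That paradigm does more than give cannabidiol: methadone is halved on Day 1, omitted on Day 2 and restarted at half dose on Day 3, and this happens in both sessions. The placebo session is what lets a reader separate what follows cannabidiol from what follows the rest of the procedure. The plan uses it in this way for adverse events and for efficacy, but not for liver enzymes, which are the only primary safety or efficacy outcome defined on one condition.

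A threshold count also discards most of the information in a laboratory value. In a small pilot, few participants may cross 3x ULN, and the count then says little about whether enzymes moved at all. What is at stake is the usefulness of the liver data to the grant application that the pilot is meant to support.

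**Working it through.** The documents give no sample size, event rate or enzyme variability, so there is no planned figure to reproduce. The check rests on the text, with arithmetic for illustration.

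**1. Is a counted case new?** Entry requires AST and ALT at or below 3x ULN. A value above 3x ULN after the active session is therefore a crossing since screening. It need not be a crossing since cannabidiol began: a placebo-first participant could have crossed during the placebo session, and no liver draw is described at admission to the second session.

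**2. What can the listed count distinguish?** Assume N = 20 or N = 12, with 2 participants crossing after cannabidiol. The exact (Clopper-Pearson) 95% limits for x of n are the 0.025 quantile of Beta(x, n − x + 1) and the 0.975 quantile of Beta(x + 1, n − x).

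| Assumed N | Crossed after CBD | Crossed after placebo | Result under 7a | Active minus placebo |
|---|---|---|---|---|
| 20 | 2 | 0 | 10% (1.2% to 31.7%) | 2/20 − 0/20 = 10 points |
| 20 | 2 | 2 | 10% (1.2% to 31.7%) | 2/20 − 2/20 = 0 points |
| 12 | 2 | 0 | 17% (2.1% to 48.4%) | 2/12 − 0/12 = 17 points |
| 12 | 2 | 2 | 17% (2.1% to 48.4%) | 2/12 − 2/12 = 0 points |

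For a given N, the result under 7a is the same in both rows, while the comparison of interest differs. This shows what the definition omits. It does not estimate an error.

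**3. What does a count of zero say?** The one-sided 95% upper bound is 1 − 0.05^(1/N): 25.9% at N = 10 and 13.9% at N = 20 (both N assumed).

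**4. What does the threshold hide?** In multiples of ULN, with assumed values:

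- 0.5 to 2.5 is a 2.5/0.5 = 5-fold rise. Since 2.5 < 3, it is not counted.
- 2 to just over 3 is a rise of just over 3/2 = 1.5-fold, and it is counted.

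**5. The stopping rule in 7d.** Its wording joins an absolute limit to a comparison with screening. Two assumed cases show that the literal readings differ:

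- 0.5 to 1.6 is 1.6/0.5 = 3.2 times baseline but not above 3x ULN.
- 2.5 to 3.1 is above 3x ULN but only 3.1/2.5 = 1.24 times baseline.

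The most natural reading is a value above 3x ULN that was not present at screening. The time point is also loose, but section 4a uses the word study for a single session in several places (for example, discharge on Day 3). On that reading every participant is assessed after cannabidiol.

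**The case against.** The strongest reply is that the existing outcome largely answers the stated aim. The aim is the safety of giving the drug in this setting, not attribution of enzyme changes. A count above a recognised limit, on active drug, in participants who were all at or below that limit at screening, tells the reader whether anyone reached a worrying level. The study is descriptive, and nothing in 7c forbids tabulating placebo-session values as well. Nor do the documents say that withdrawal or methadone re-dosing raises AST or ALT; the methadone effects listed in section 8a include no hepatic one.

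Most of this stands, and it limits the point. The outcome is not wrong as written, and no confounder is shown. But a case that is new since screening is still uncontrolled, and 7c names the listed outcomes as the data for the application, so the listing matters. Permission to tabulate the placebo values is weaker than a statement made before results are seen that they will be tabulated.

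A reader might also infer that the stopping rule would miss liver elevations after cannabidiol. The documents do not support that. On the single-session reading nobody is missed. The post-cannabidiol value is itself the 7a outcome, section 8c states that "All study events will be monitored during weekly meetings between the study investigators", and 7d allows a participant to be discharged "if new information becomes available to suggest this study may cause them more than minor harm". Any probability that the rule fires would rest on an assumed sample size and assumed event rates, so it would not measure a fault in this plan.

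**Conclusion.** The point holds for 7a as an inexpensive improvement that should be made. As listed, the primary liver outcome gives no active-placebo comparison and no size of change, although the design provides the control and the draws appear to be taken in both sessions. That last step is an inference from the general wording of section 4a and should be confirmed.

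The size cannot be expressed as a bias or a loss of power, because the documents give no sample size or rates; the sample sizes, counts and enzyme values used for illustration are assumptions. Three stronger conclusions are not supported: that the 3x ULN limit is unsuitable, that the outcome has no baseline, or that placebo values will go uncollected. The 7d wording is a clarification of minor weight and adds nothing to the importance of the main point.

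**What to change.** In section 7a, replace the liver bullet with:

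> AST and ALT at the end of each session, by condition (0, 800 mg CBD), with number tested: number >3x ULN; change and fold-change from screening; within-participant active-minus-placebo difference, shown by sequence; all descriptive.

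Screening should serve as the baseline, because it is the only pre-dose liver value described and a value taken just before session 2 would follow cannabidiol in active-first participants.

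The cost is protocol wording and one more table, with no extra visit, sample or test if the draws are taken in both sessions as they appear to be. The main downside is carry-over: if enzymes have not recovered within the interval of at least one week, the active-minus-placebo difference is diluted in active-first participants, which is why results are shown by sequence. Participants who complete one session contribute to the by-condition figures but not to the difference, so the number tested should accompany each figure.

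In section 7d, state that the liver criterion means a value >3x ULN at the end of a session in a participant who was at or below that limit at screening. This costs one sentence. The limit and the number five can stay as the investigators set them.

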Methadone Valuation Task: The morning of Day 3, participants will complete baseline withdrawal ratings and be presented with the opportunity to take 50% of their usual methadone maintenance dose or earn money. For every 60 minutes up to 14:00 that the participant does not take the dose, they will earn a small amount of money (Total potential earnings= \$100). At the end of the period, all participants who have not yet requested their methadone dose will receive it. All Day 3 methadone doses will be 50% of the participant's prescribed dose. Participants will be required to remain on the unit under observation until JHMIRB eFormA 01 Version 3 Dated: 06/2007

17:00 to provide sufficient opportunity for peak effects of methadone to occur. At that time, all participants who show no signs of respiratory distress (SP02<96, respiration rate <8 breaths per minute) and feel safe to leave will be discharged.

All participants will be required to stay in the unit until 17:00, to prevent them from selecting methadone in order to end the study prematurely and to provide an opportunity for withdrawal to decrease in severity before they leave. The purpose of this task is to assess the objective, behavioral economic value the participant places on methadone as a withdrawal-relieving medication following accumulated exposure to Epidiolex vs. placebo. We have developed this task by translating preclinical methodology and we will use this opportunity to determine whether this task is an appropriate method to include in a formal R01 application.

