Cue-concurrent Choice Task: The effects of opioid-related cues on concurrent choice will be evaluated using a cued concurrent choice task. Participants will be instructed that they will be asked to make choices about different amounts of money that they would like to earn. Participants will be instructed that they should consider the choices carefully because they will randomly receive five of the monetary outcomes they chose. This task consists of a series of trials in which concurrent choice is evaluated between two monetary values (e.g., \$0.10 versus \$0.05). Each concurrent choice is immediately preceded by two visual stimuli presented side-by-side. On opioid trials, one image is opioid-related and the other is a paired neutral image. Opioid-related images include depictions of prescription pills or heroin and/or related drug paraphernalia. Paired neutral images are chosen to match the number of objects, color, and size of opioid images. On neutral filler trials, both images are unrelated to opioids or opioid paraphernalia (e.g., furniture pieces). All trials begin with a fixation point presented for 1000 ms in the center of the screen. The two visual stimuli then replaced the fixation point and are displayed for 2000 ms. Finally, a monetary value appears below each image and participants are instructed to select the monetary reinforcer they want to receive. Participants will receive their money choices from 20 random trials which could earn them an additional \$5. Potential earnings will be explained prior to starting the task to increase engagement with the task.

Methadone Reinduction: At the end of the Methadone Valuation Task, all participants who have not yet requested the methadone dose will receive their dose. All Day 3 methadone doses will be 50% of the participant's prescribed dose. Participants will be required to remain on the unit under observation until 17:00 to provide sufficient opportunity for peak effects of methadone to occur. At 17:00, all participants who show no signs of respiratory distress (SP02<96, respiration rate <8 breaths per minute) and feel safe to leave will be discharged. Any participant who is unable to leave will be observed until he/she is safe ot

leave or will be readmitted to the CRU one additional night. Participants will be expected to return to routine care upon methadone reinduction and study discharge.

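### The Day 3 SOWS area under the curve has no cut-off at the self-timed methadone dose, so its CBD-placebo difference partly reflects when methadone was taken

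*Combined protocol and SAP*

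**What the plan says.** Section 7a, Initial Efficacy, compares the CBD and placebo sessions on SOWS withdrawal ratings: "Scores will be evaluated using area-under-the-curve for each day as well as peak daily rating". Neither 7a nor the statistical plan in 7c sets a rating window or says what to do with ratings taken after methadone.

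The Day 3 timeline is in section 4a:

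- Session Procedures: "Withdrawal ratings will continue up to study discharge on Day 3". Ratings are taken about every 4 hours while the participant is awake.
- Methadone Valuation Task, Day 3 morning: "participants will complete baseline withdrawal ratings and be presented with the opportunity to take 50% of their usual methadone maintenance dose", or to earn money instead. "For every 60 minutes up to 14:00 that the participant does not take the dose, they will earn a small amount of money".
- Methadone Reinduction, at the end of the task: "all participants who have not yet requested the methadone dose will receive their dose".
- Session Procedures also lets a participant resume methadone at any earlier point. Anyone who does so before the task begins is excluded from it.

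The waiting time is scored in section 7a as a second efficacy outcome: "Number of 30-minute intervals for which the participant selected money over methadone during the methadone evaluation task".

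Section 6a omits the Day 2 methadone dose. Section 7c says results will be mainly descriptive and will serve as preliminary data for an R01 application.

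**The concern.** Methadone treats the symptom being measured, and section 4a expects withdrawal to ease during the stay after it is given. A full-day Day 3 AUC therefore adds an untreated stretch to a treated stretch, and the participant decides where one ends and the other begins. The crossover does not remove this, because the same person can wait for different times in the two sessions. The task exists to find out whether CBD changes that wait.

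The AUC and the waiting time are thus two readings of one process. If CBD helps people hold out longer, the longer untreated stretch raises the CBD-session AUC and counts against CBD. If they take methadone sooner on CBD, the AUC tends to flatter it. At stake is a Day 3 difference, in either direction, being carried into the grant application as a CBD effect when part of it is methadone timing.

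**Working it through.** **No figure to reproduce.** The plan states no SOWS values, variance, effect size or sample size, and the figure showing rating times is not available. The mechanism comes from the text above. The numbers below only illustrate it.

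**Inputs from the documents.** Methadone is given by 14:00 at the latest, the stay lasts until 17:00 (Methadone Valuation Task), and methadone peaks 1 to 7.5 h after an oral dose (section 6a).

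**Assumptions.** Day 3 ratings start at 06:00. The untreated score is a flat 30. After methadone it falls in a straight line over *d* hours to a fraction *k* of its level. Placebo-session methadone is at 09:00 unless stated. In the worked case *k* = 1/2, *d* = 2, and CBD scales the whole curve.

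**Formula.** AUC = base × (dose time − 6) + *d* × (base + end)/2 + end × (17 − dose time − *d*).

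| Session | Dose time | AUC |
|---|---|---|
| No CBD effect | 09:00 | 30×3 + 2×22.5 + 15×6 = 225 |
| No CBD effect | 11:00 | 30×5 + 2×22.5 + 15×4 = 255 |
| CBD, true −20% | 09:00 | 24×3 + 2×18 + 12×6 = 180 |
| CBD, true −20% | 11:00 | 24×5 + 2×18 + 12×4 = 204 |
| CBD, true −20% | 14:00 | 24×8 + 2×18 + 12×1 = 240 |

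**Results.**

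- No CBD effect, 2 h longer wait on CBD: 255/225 − 1 = +13.3%. With a 2 h shorter wait: 225/255 − 1 = −11.8%.
- True −20%, equal waits: 180/225 − 1 = −20.0%. CBD 2 h later: 204/225 − 1 = −9.3%. CBD at 14:00: 240/225 − 1 = +6.7%, a change of sign. CBD 2 h earlier (placebo 11:00): 180/255 − 1 = −29.4%.
- If methadone instead brings both sessions to the same floor of 15, equal waits give (24×3 + 2×19.5 + 15×6)/225 − 1 = 201/225 − 1 = −10.7%. So equal waits leave the effect intact or shrink it, depending on how the two drugs combine.

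Over *k* = 1/3, 1/2, 2/3 and *d* = 1, 2, 4, 7.5 h, the no-effect case with a 2 h longer wait gives +6.4% to +22.2%.

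**Sensitivity to rating times.** Ratings come about every 4 hours, so the planned AUC would be a trapezoid on a few points. Take no CBD effect and a wait 1 h longer on CBD (10:00 against 09:00), still with *k* = 1/2 and *d* = 2:

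- Ratings at 08:00, 12:00 and 16:00: both sessions read 30, 15, 15, so the difference is 0.
- Ratings at 06:00, 10:00, 14:00 and 17:00: placebo reads 30, 22.5, 15, 15 (105 + 75 + 45 = 225) and CBD reads 30, 30, 15, 15 (120 + 90 + 45 = 255), so the difference is +13.3%.

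Over all twelve combinations the first grid gives 0 to +14.3% and the second +3.7% to +53.3%.

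**Peak.** If withdrawal rises by a fraction *r* of its 06:00 value per hour until methadone, peak = base × [1 + *r* × (dose time − 6)]. With true −20%, placebo at 09:00 and *r* = 5%, CBD at 11:00 gives (0.8 × 1.25)/1.15 − 1 = −13.0%. With *r* = 8% and CBD at 14:00 it is (0.8 × 1.64)/1.24 − 1 = +5.8%.

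**Pre-offer ratings.** Before the offer both sessions are on study drug alone, so ratings at the same clock times return the assumed effect in every case, provided nobody has resumed methadone earlier.

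**The case against.** The strongest reply is that section 7a does not actually say that post-methadone ratings enter the Day 3 AUC. The outcome is called symptom suppression, and the SOWS feasibility outcome is confined to abstinence-induced withdrawal. A full-day AUC is also a legitimate summary of CBD together with the participant's own methadone use, if labelled so. Results are descriptive, Day 2 is reported, and the money-over-methadone count sits beside the AUC. Pre-offer ratings are few and come early.

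Much of this stands. The full-day summary need not be dropped, and the consequence is modest. The first part does not rescue the plan: an AUC for each day, with ratings to discharge and no cut-off, includes the post-methadone ratings when followed as written. Descriptive status avoids a false significance claim but does not correct a biased estimate.

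Three stronger readings are tempting and not supported:

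- *The Day 3 AUC is biased against CBD.* The direction depends on which session has the longer wait, which is unknown.
- *The illustrations measure the size or likelihood of reversal.* They rest on assumed scores, waits and rating times, and moving the rating grid alone takes the bias from zero to large.
- *Day 1 is distorted in the same way.* Ratings before the first study-drug dose occur in both sessions and cancel in expectation from an absolute AUC difference. Dilution appears only if the difference is expressed as a percentage of the whole-day AUC, which the plan does not specify.

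**Conclusion.** The point holds and should be fixed. As written, the Day 3 SOWS AUC compares sessions that may differ in methadone timing as well as in study drug. The peak has the same fault if withdrawal is still rising during the wait. The Day 3 contrast can understate, reverse or overstate a CBD effect. Its size is unknown: on assumed values it ranges from no bias to a change of sign, driven by the difference in waits and by the rating times.

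The harm is limited to a misleading Day 3 estimate in the R01 preliminary data; no error rate is affected. Day 2 is the better SOWS comparison because no methadone is scheduled. It is not perfectly clean, since early resumption is allowed and section 8a expects CBD to delay withdrawal onset through methadone metabolism.

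**What to change.** In section 7a:

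1. Base the Day 3 CBD efficacy summary on ratings taken before the methadone offer, at the same clock times in both sessions, including at least the Day 3 baseline rating. If only one such rating exists, report that score and not an AUC.
2. Keep the full-day Day 3 AUC and peak only as a supportive summary labelled *CBD plus self-chosen methadone*, shown with methadone time by session.
3. Present Day 2 AUC and peak as the main SOWS comparison without scheduled methadone. Report early methadone resumption by session and time, and show results with and without the affected participants.

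**Cost.** No new type of data is needed, but the rating schedule in section 4a may need fixed pre-offer clock times, because neither the offer nor the ratings have firm ones. Day 3 efficacy may rest on one or two ratings. These probably precede the fourth dose's peak: a first dose near 18:00 on Day 1 plus 3 × 12 h puts the fourth near 06:00 on Day 3, and the 5 to 6 h to peak that section 6a gives for 750 mg points to about 11:00 to 12:00.

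**Separately, reconcile two conflicts.** The task pays per 60 minutes in section 4a but is scored in 30-minute intervals in section 7a. Session Procedures says "Participants will be discharged in the afternoon on Day 3, one hour after finishing the Methadone Valuation Task", while the task description says "All participants will be required to stay in the unit until 17:00". With the task ending by 14:00, the first implies discharge by 15:00, so the two statements give different rating windows.
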